	15.	Active systemic infection, including active endocarditis;
		Page 11 of 113

16.	Untreatable hypersensitivity or contraindication to any of the following: Aspirin and Clopidogrel and Ticlopidine, OR Heparin and Bivalirudin, or Warfarin, OR Nitinol Alloys (nickel and titanium) or contrast media;
17.	Any recent percutaneous coronary, carotid, endovascular intervention, carotid surgery, or cardiac surgery;
18.	Recent implant or revision of any rhythm management device (i.e., pacemaker, cardiac resynchronization therapy [CRT] with or without cardioverter-defibrillator [CRT-D]);
19.	Resting systolic blood pressure < 90 or > 160 mmHg after 3 consecutive measurements;
20	Recent CVA or TIA;
21.	Previous stroke with permanent disability (modified Rankin score > 2);
22.	Severe renal insufficiency with eGFR ≤ 25 mL/min or requiring chronic renal replacement therapy;
23.	Contraindication to transseptal catheterization;
24.	Concurrent medical condition with a life expectancy of less than 12 months in the judgment of the investigator;
25.	Pregnant or planning pregnancy within next 12 months;
26.	Known bleeding or clotting disorders or patient refuses blood transfusion;
27.	Severe COPD in whom the primary mechanism of dyspnea is pulmonary disease rather than heart failure;
28.	Recent myocardial infraction (per WHO definition);
29.	Patient has been approved to participate and is currently enrolled in, or has participated in another investigational drug or device clinical study where the primary study endpoint was not reached at time of enrollment;
30.	Any condition, in the opinion of the Investigator, making it unlikely the patient will be able to complete all protocol procedures

	(including compliance with guideline directed medical therapy) and follow-up visits;
31.	Other medical, social, or psychological conditions that preclude appropriate consent and follow-up, including patients under guardianship.

Co-primary endpoint I

Sample Size & Endpoint Analysis

Using PASS software and a test for two independent proportions 375 enrolled patients with up to 20% attrition provides > 99% power to detect a difference between the groups using the following assumptions:

- 1. Proportion in control arm who meet the criteria for MR reduction (MR \leq 2+) is 10%.
- 2. Proportion in treatment arm who meet the criteria for MR reduction (MR \leq 2+) is 70%.
- 3. A two-sided significance level (alpha) of 0.05.

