6.7 Technical Feasibility Assessment of Edwards Cardioband System Implantation by **Sponsor**

The Sponsor will review applicable patient data collected at Screening and Baseline Visits (e.g. cardiac CT) to determine the technical feasibility of implanting the Edwards Cardioband System. The Sponsor may also assist the site in determining the most appropriate implant size for the patient.

Central Screening Committee Determination

After the Central Screening Committee (CSC) has reviewed all screening and baseline assessments and reached a decision on eligibility, the decision will be communicated to the site. The site will proceed to scheduling the case for approved patients in accordance with institutional procedures.

^{*}If TTE is more than 60 days from the procedure, a repeat TTE will be required.

Randomization Procedure 7

Patients will be prospectively randomized into the clinical study. Randomization will occur only after the patient provides informed consent, completes all required screening and baseline procedures, and satisfies the study eligibility criteria (including eligibility determination by the Central Screening Committee). Randomization shall be performed after cases have received final approval from the CSC and Sponsor and the case has been scheduled at the institution.

Eligible patients will be randomly assigned in a two to one (2:1) ratio to either treatment with Edwards Cardioband System + Guideline Directed Medical Therapy (Device Group) versus Guideline Directed Medical Therapy alone (Control Group).

Randomization assignment will be generated via the randomization module of the EDC system. Randomization scheme will be based on random blocks and will be stratified by:

- study center
- baseline ischemic vs. non-ischemic disease

This randomization schedule (list) will be masked to study patients, site personnel, study team and Sponsor. Only the un-blinded statistician and designates will be privy to the masked randomization scheme.

A patient is not considered randomized until the randomization assignment has been dispensed. If at any time after randomization a patient becomes ineligible or withdraws, the patient is still considered randomized.

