#### 2.3 Randomization and Blinding

Randomization is ideally performed within seven days prior to the scheduled procedure, but no more than 14 days prior. If a patient is randomized to Control, the scheduled interventional case is cancelled and the patient is notified that they have been enrolled in the Control/medical therapy arm of the trial and will not need to undergo an interventional procedure. The process of randomizing after a case is scheduled has been implemented to ensure that the time frame between randomization and actual treatment is minimized. Eligible patients will be randomly assigned in a 2:1 ratio to either Device group or Control group, respectively.

Randomization schedule will be generated using the Balance module in Medidata RAVE, the Electronic Data Capture System for the study. Randomization will be stratified by (a) site and (b) baseline ischemic vs non-ischemic disease. This randomization schedule will be masked to patients, site personnel, study team, and sponsor as defined in the Randomization and Blinding Plan. Only the unblinded statistician and designates will be privy to the masked randomization scheme.

All analyses of data by the study statistician/programmer will be conducted blinded to treatment assignment (similar to the conduct of blinded clinical study to the extent possible), until the time of database lock for the primary endpoint analysis. Analyses of unblinded data such as DSMB analysis will be performed by a separate non-study or independent statistician/SAS programmer.

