### 8. STATISTICAL ANALYSIS OF STUDY ENDPOINTS

### 8.1 Co-Primary Hypothesis 1

H0:  $P_{Device}(T=1) - P_{Control}(T=1) = 0$ H1:  $P_{Device}(T=1) - P_{Control}(T=1) \neq 0$ 

where

H₀	= Null hypothesis
H1	= Alternative hypothesis
P Device	= Proportion of patients in the Device group with $MR \le 2+$ at 1 year
P Control	= Proportion of patients in the Control group with MR $\leq$ 2+ at 1 year
Т	= Time (years)

The co-primary hypothesis 1 tests the superiority in reducing MR of the Device group relative to the Control group via Chi-Square test for two independent proportions with two-sided alpha = .05. Co-primary efficacy endpoint 1 must meet statistical significance in order to proceed to co-primary efficacy endpoints 2. This approach does not require any adjustment for multiplicity.

### 8.2 Co-Primary Hypothesis 2

 $H_0$ : None of the four co-primary endpoints 2 are improved by treatment  $H_1$ : At least one of the four co-primary endpoints 2 is improved by treatment

- i. Time to all-cause death within the first year
- ii. Number of heart failure hospitalizations within the first year
- iii. Improvement in Six Minute Walk Test (6MWT) at 1 year relative to baseline (≥ 40 meters improvement)
- iv. Improvement in Kansas City Cardiomyopathy Questionnaire (KCCQ) at 1 year relative to baseline (≥ 10 points improvement)

The co-primary hypothesis 2 tests the superiority of the Device group relative to the Control group for the hierarchical sequence of the four co-primary endpoints 2 via the Finkelstein-Schoenfeld test (Finkelstein and Schoenfeld, 1999). The Finkelstein-Schoenfeld test is a generalization of the Gehan Wilcoxon test. Each patient pair is compared in descending order of the endpoints until one member of the pair shows superiority. While the example comparison given in the table below shows a Device patient being compared to a Control patient it should be noted that a pairwise comparison is made for every patient in Device group versus every patient in Control group.

THIS DOCUMENT CONTAINS CONFIDENTIAL AND PROPRIETARY INFORMATION OF EDWARDS LIFESCIENCES, LLC. IT MUST NOT BE REPRODUCED OR DISCLOSED TO THIRD PARTIES WITHOUT PRIOR WRITTEN PERMISSION OF EDWARDS LIFESCIENCES, LLC. (This template is required by DOC.))

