The Finkelstein-Schoenfeld method is a simple non-parametric statistical test for analyzing the impact of treatment which combines multiple events (e.g., death and hospitalizations) with longitudinal measures of clinical effect (e.g., 6MWT and KCCQ). The test is based on a Wilcoxon rank sum test. We define a score,  $\mu_{ij}$ , which is chosen to reflect whether patient i has had the more favorable outcome than patient j by following the hierarchy of scoring provided in table 1. If one of the patients has the more favorable outcome, his score is +1 and the other patient has a score of -1. If it is not possible to assign either patient as having the better outcome, then both patients get a score of 0.

This is a score test based on the sum of scores for the Device group. Suppose there are N total patients in the trial, let  $D_i = 1$  for patients in Device group and  $D_i = 0$  for patients in the Control group. Using the  $\mu_{ij}$  for every pair of patients defined above, we assign a score to each patient,  $U_i = \sum_{i \neq j} \mu_{ij}$ . The test is now based on

$$T = \sum_{i=1}^{N} U_i D_i.$$

Finkestein and Schoenfeld refers to this test as the generalization of the Gehan Wilcoxon (GGW) test. The null hypothesis is that none of the endpoints in table 1 are different between Device and Control group. The alternative hypothesis is that at least one endpoint in table 1 is different between Device and group.

Let m be the number of patients in the Device group. The mean of T is zero and its variance is

$$V = \frac{m(N-m)}{N(N-1)} (\sum U_i^2).$$

The hypothesis of interest is tested by comparing  $L = \frac{T}{\sqrt{V}}$  to the normal distribution. Hence, we are looking for a z-score that is indicative of a significant difference (p < .05) between the Device and Control groups.

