### 8.11 Determination of Sample Size

Co-primary endpoint 1

Using PASS software and a test for two independent proportions 375 enrolled patients give us >99% power to detect a difference between the groups using the following assumptions:

- 1. Proportion in control arm who meet the criteria for MR reduction (MR  $\leq$  2+) is 10%.
- 2. Proportion in treatment arm who meet the criteria for MR reduction (MR  $\leq$  2+) is 70%.
- 3. A two-sided significance level (alpha) of 0.05.
- 4. A 2:1 treatment allocation ratio between Edwards Cardioband System (Device group) and control group.
- 5. Data will be available for 60% of the randomized patients (accounting for mortality and lost to follow-up).

#### Co-primary endpoint 2

Assuming up to 20% dropout, a total of 375 enrolled patients will ensure at least 300 patients with evaluable data. Based on 5,000 trial simulations using SAS software (version 9.4), it is estimated that 300 evaluable patients will provide 87% power to detect superiority of treatment vs. control using the Finkelstein-Schoenfeld test and the following assumptions:

- 1. All-cause mortality of 20% within the first year in both groups (Control and Device).
- 2. Cardiovascular mortality of 15% within the first year in both groups (Control and Device).
- 3. Number of heart failure hospitalizations within the first year:
  - a. 60% of the patients in the Control and 70% in the Device group will not have HF hospitalization.

THIS DOCUMENT CONTAINS CONFIDENTIAL AND PROPRIETARY INFORMATION OF EDWARDS LIFESCIENCES, LLC. IT MUST NOT BE REPRODUCED OR DISCLOSED TO THIRD PARTIES WITHOUT PRIOR WRITTEN PERMISSION OF EDWARDS LIFESCIENCES, LLC. (This template is required by DOC

E	Revision Date: February 28, 2019		Rev		For Use Only by Affiliates of Edwards Lifesciences	Page 17 of 18
Edwards	Title	Statistical Analysis Plan for ACTIVE 2017-05				

- b. 10% of the patients in the Control group and 10% of the patients in the Device group will have one HF hospitalization.
- c. 10% of the patients in the Control group and 5% in the Device group will have two HF hospitalizations.
- d. 10% of the patients in the Control group and 5% in the Device group will have three HF hospitalizations.
- e. 5% of the patients in the Control group and 5% in the Device group will have four HF hospitalizations.
- f. 5% of the patients in the Control group and 5% in the Device group will have five or more HF hospitalizations.

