- Improvement in 6-minute walk test at one year vs. baseline:
   10% of the patients in the Control group and 50% of the patients in the Device group will have an improvement in 6 minutes walking distance of 40 meters or more compared to their baseline result.
- Improvement in KCCQ score at one year vs. baseline:
   10% of the patients in the Control group and 50% of the patients in the Device group will have an improvement in KCCQ score of 10 points or more compared to their baseline result.
- 6. A two-sided significance level (alpha) of 0.05.
- 7. A 2:1 treatment allocation ratio between Device group and Control group.

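### The co-primary II Finkelstein-Schoenfeld test ignores the etiology stratum used in randomisation: it is valid, but gives up about 0 to 2 points of power, depending on how prognostic etiology is

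*SAP*

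**What the plan says.** SAP 2.3: "Randomization will be stratified by (a) site and (b) baseline ischemic vs non-ischemic disease". Protocol 7 names the same two factors, study center and "baseline ischemic vs. non-ischemic disease", and allocates in random blocks.

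Neither co-primary test refers back to these strata. SAP 8.1 uses a "Chi-Square test for two independent proportions with two-sided alpha = .05". SAP 8.2 says of the Finkelstein-Schoenfeld (FS) test: "This is a score test based on the sum of scores for the Device group". Each patient's score U_i is summed over all other patients, and T, the Device total, is divided by the square root of one pooled variance V. No stratum term appears.

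No stratified primary or sensitivity analysis is specified elsewhere. Protocol 13.4.1 leaves covariate analyses to be pre-specified in the SAP. SAP 6.1 says only that they may be done and names none. SAP 10 does not list this among the differences from the protocol.

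**The concern.** V is the permutation variance that applies when any m of the N patients could have been the Device group. Stratified randomisation is more restrictive: it aims to hold the Device share at two thirds within each etiology group. If ischemic and non-ischemic patients differ in outcome, part of the spread in U_i lies between strata. Balanced allocation keeps that part out of T, but it remains in V. The ratio T/sqrt(V) is then too small on average, and some pairs are decided by etiology rather than by treatment.

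Co-primary II is where this could matter. It is the co-primary test with power to lose, it must succeed before the eight key secondary endpoints are tested (Protocol 13.4.4), and its conditional power drives the sample-size re-estimation in SAP 8.10, where a value below 90% prompts an increase.

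**Working it through.** **Inputs from the documents.** SAP 8.11: "A two-sided significance level (alpha) of 0.05"; "A 2:1 treatment allocation ratio between Device group and Control group"; 300 evaluable for co-primary II, hence 200 Device and 100 Control; one-year mortality 20% in both arms; HF hospitalisation counts 0/1/2/3/4/5+ of 60/10/10/10/5/5% (Control) and 70/10/5/5/5/5% (Device); 6MWT and KCCQ response 10% versus 50%. For co-primary I, 10% versus 70%, with "Data will be available for 60% of the randomized patients (accounting for mortality and lost to follow-up": 0.60 × 375 = 225, or 150 versus 75.

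**Assumptions.** Ischemic share 30% to 70%; between-stratum gaps in mortality and in HF-hospitalisation-free share as listed below; independent components; all-cause death at step 1; exact 2:1 balance within strata.

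**1. The plan's own figures.** Co-primary I: pooled proportion (0.70 × 150 + 0.10 × 75)/225 = 0.50. Null standard error sqrt(0.25 × (1/150 + 1/75)) = 0.0707. Alternative standard error sqrt(0.21/150 + 0.09/75) = 0.0510. Power = Φ((0.60 − 1.96 × 0.0707)/0.0510) = Φ(9.0), effectively 100%, so the stated >99% reproduces. Co-primary II: simulating T/sqrt(V) at 200:100 gives 93.6%. This agrees with the synopsis (>90%). The 87% in SAP 8.11 and Protocol 13.5 does not reproduce at 300 evaluable (240 evaluable gives 87.2%); that is a separate inconsistency.

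**2. Why V can be too large.** SAP 8.2 has V = [m(N−m)/(N(N−1))] × ΣU_i². Split the sum by stratum s:

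ΣU_i² = Σ_s Σ_(i in s) (U_i − Ū_s)² + Σ_s N_s Ū_s²

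With exact 2:1 balance in each stratum, the second term adds nothing to the true variance of T, so true variance/V is roughly 1 minus the between-stratum share. If etiology is not prognostic, that share is about zero and V is right.

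**3. Null behaviour, 50/50 strata (20,000 trials).**

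| Mortality / HFH-free gap (points) | True variance of z | Two-sided error |
|---|---|---|
| 5 / 5 | 1.00 | 5.0% |
| 10 / 20 | 0.95 | 4.3% |
| 20 / 30 | 0.89 | 3.7% |

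Check on the last row: 1.96/sqrt(0.89) = 2.08, which has a two-sided tail of about 3.8%. With gaps of 24/30 the error is 3.3% unstratified and 4.8% stratified. No scenario inflates it.

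**4. Power at 50% versus 10% response.** The statistic T/sqrt(V) is compared with the same scores formed within etiology stratum and combined with weights.

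| Share; gaps | Weights | Unstratified | Stratified |
|---|---|---|---|
| 50%; none | 1/(N+1) | 93.6% | 93.6% |
| 50%; 5/5 | 1/(N+1) | 93.9% | 93.9% |
| 50%; 10/10 | 1/(N+1) | 93.8% | 94.3% |
| 50%; 10/20 | 1/(N+1) | 95.0% | 95.9% |
| 50%; 20/30 | 1/(N+1) | 96.1% | 97.9% |
| 50%; none | 1/N | 93.3% | 93.4% |
| 50%; 12/16 | 1/N | 95.0% | 95.8% |
| 50%; 24/30 | 1/N | 96.6% | 98.4% |
| 30%; none | 1/N | 93.0% | 93.0% |
| 70%; none | 1/N | 93.3% | 93.1% |
| 70%; 24/30 | 1/N | 96.9% | 98.3% |

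The 1/(N+1) rows use 20,000 trials and the 1/N rows 6,000, where the standard error of one figure is sqrt(0.94 × 0.06/6,000) = 0.3 points. A further 6,000-trial run with 1/N weights and 50/50 strata gave 94.0% against 93.5% with no prognosis, 94.5% to 95.4% at 12/16 and 96.9% to 98.3% at 24/30.

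**5. The weights matter.** Adding T_s and V_s unweighted, with a 30/70 split and no prognostic effect, cuts power from 93.6% to 91.1%. If the smaller stratum also has the better prognosis, power falls to 86–89%, against 94–96% unstratified.

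**6. Co-primary I.** At 150 versus 75, with gaps of 0 to 40 points between strata, chi-square and Cochran-Mantel-Haenszel both give 100.0%.

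**7. Site.** 75 sites × 2 etiologies = 150 cells; 375/150 = 2.5 patients per cell, too sparse for within-cell scoring.

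**The case against.** The best defence is that nothing is invalid. The pooled test never exceeds its nominal error rate, and any conservatism works against the device. The documents give no ischemic share and no outcome difference by etiology, so a prognostic effect is conjecture. Balance within etiology is also looser than assumed above: blocks are filled within about 150 small cells, many will be incomplete, and the mITT population (SAP 4.3) drops Device patients who were not implanted. With blocks of 3 and 6 (assumed), uneven sites and 20% attrition, the one-sided error of the pooled test was 2.2% under strong prognosis and 2.3% under moderate, close to the nominal 2.5%. All of this stands. It limits the size of the point. It does not supply a reason to ignore a recorded stratification factor.

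Three stronger readings are tempting and not supported:

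- **That the variance is too large outright.** This holds only if etiology is prognostic.
- **That both co-primary tests lose power.** Co-primary I has none to lose.
- **That the loss is about 5 points.** A gain of that size (85.8% to 90.7%, gaps 24/30) appears only if Device response on 6MWT and KCCQ is set at 38%, a figure in neither document. At the documented 50% the same gaps give 96.6% to 98.4%.

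**Conclusion.** The point holds as one of efficiency, not validity, and for co-primary II only. The FS test ignores a factor on which patients were randomised. At the SAP's assumptions the cost is 0 points of power if etiology is not prognostic, about 1 point if moderately prognostic and about 1 to 2 points if strongly prognostic. Stratifying with 1/N weights showed no loss beyond simulation noise when etiology has no effect.

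These sizes rest on assumed etiology shares and prognostic gaps, independent components and exact balance within strata. Incomplete blocks and mITT exclusions may shrink the effect; this was checked for the conservatism but not for power.

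**What to change.** **SAP 8.2.** Compare pairs only within the ischemic or the non-ischemic stratum, as recorded at randomisation. For each stratum s, with N_s patients of whom m_s are Device, compute U_i over that stratum, T_s = ΣU_i D_i and V_s = [m_s(N_s−m_s)/(N_s(N_s−1))] × ΣU_i². Refer

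L = Σ(T_s/N_s) / sqrt(Σ(V_s/N_s²))

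to the normal distribution. State the weights explicitly, since an unweighted sum can lose power when the strata are unequal. Leave site out of the analysis strata and say why.

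**SAP 8.10.** Use the same statistic in the conditional-power simulation, so that the interim evaluates the test that will be run.

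**SAP 8.1 (optional).** A Cochran-Mantel-Haenszel test stratified by etiology would be consistent with the design; it adds no power.

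If the sponsor keeps the pooled FS test as primary, the minimum is to give the reason and name the weighted stratified version as a sensitivity analysis, which would also go some way to meet the commitment in Protocol 13.4.1.

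The cost is SAP wording and a few lines of code, before unblinding. No new data are needed, because the stratum is known for every randomised patient.

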### 8.3 Primary and Secondary Safety Endpoints (30 Days)

Overall rates of device and procedure related major adverse events (MAEs) though 30 days post procedure (i.e., primary safety endpoints) as well as the components will be calculated, along with 95% confidence intervals.

### 8.4 Key Secondary Efficacy Endpoints (1 Year)

Secondary efficacy endpoints will be tested in hierarchical order after the primary endpoints to address multiplicity and preserve alpha at the .05 level. When one of the endpoints does not achieve statistical significance in favor of the Device group, no further testing of subsequent endpoints will be conducted.

### a. Mitral regurgitation (MR)

Superiority test of Device group versus Control group via the chi-square statistic, for the difference in the prevalence of  $MR \le 1+$  at one year, with a two-sided alpha of 0.05. The null (H0) and alternative (H1) hypotheses are:

THIS DOCUMENT CONTAINS CONFIDENTIAL AND PROPRIETARY INFORMATION OF EDWARDS LIFESCIENCES, LLC. IT MUST NOT BE REPRODUCED OR DISCLOSED TO THIRD PARTIES WITHOUT PRIOR WRITTEN PERMISSION OF EDWARDS LIFESCIENCES, LLC. (This template is required by DOC.))

	2017-05 Sta	tistical Analysis Plan			1.0   7/16/20	19
$\mathbb{P}$	Revision Date: Febr	uary 28, 2019	Rev		For Use Only by Affiliates of Edwards Lifesciences	Page 14 of 18
Edwards	Title	Statistical Analysis Plan for ACTIVE 2017-05				

H0: PDevice - PControl = 0

 $H_1: P_{\text{Device}} - P_{\text{Control}} \neq 0$ 

 $P_{Device}$  and  $P_{Control}$  are the prevalence of MR  $\leq$  1+ at one year in the Device and Control groups, respectively.

#### b. New York Health Association (NYHA)

Superiority test of Device group versus Control group via the Chi-square statistic, for the difference in the proportion of subjects with NYHA class I/II at one year, with a two-sided alpha of 0.05. The null (H0) and alternative (H1) hypotheses are:

H0:  $P_{Device} - P_{Control} = 0$ H1:  $P_{Device} - P_{Control} \neq 0$ 

PDevice and PControl are the proportion of subjects with NYHA I/II at one year in the Device and Control groups, respectively. Fisher's Exact Test will be performed if assumptions for the Chi-square test are not met.

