6.2 Inclusion Criteria

Patients must meet all of the following criteria to be eligible for the study:

Inclusion	Criteria	Window/Guidance
Criteria #		
1.	Eighteen (18) years of age or older;	As of date of signature on informed consent
2.	Clinically significant functional MR (≥ 3+ by echocardiography) as assessed by the core lab;	
3.	Stable heart failure medications as determined by local heart team;	Stable for 30 days prior to procedure date (further details in Section 8.3)
4.	Elevated BNP > 150 pg/ml or corrected NT-proBNP > 600 pg/ml within past 90 days or heart failure hospitalization within past 12 months;	Elevated BNP or NT-proBNP measured no earlier than 90 days prior to date of informed consent OR heart failure hospitalization within past 12 months prior to informed consent.
5.	Symptomatic heart failure patients with measured baseline 6 minute walk test (6MWT) between 150 and 400 meters;	
6.	Patient is deemed appropriate for Edwards Cardioband System by the Heart Team at the investigational site and the Central Screening Committee;	
7.	Patient is able and willing to give informed consent and follow protocol procedures, and comply with follow-up visit compliance.	

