### 3.6 Secondary Endpoints – Powered (1 Year)

The following key secondary efficacy endpoints will be tested between Device and Control group in hierarchical order to account for multiplicity:

- a. MR ≤ 1+
- b. NYHA class
- c. KCCQ
- d. 6MWT
- e. SF-36v2 Health Survey (SF-36)
- f. Heart failure hospitalizations
- g. Cardiovascular death
- h. All-cause mortality

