Survival analysis techniques will be used to analyze the time-to-event variables. Patients without events will be censored at their last known event-free time point. If this event-free time point occurs after the analysis time point, the days to event variable will be set equal to the analysis time point so that the patient will be included in the analysis. For patients who did not have an event or early withdrawal and have not yet completed the analysis visit, they will be censored at the time of their last follow-up. Time to first event curves will be constructed using Kaplan-Meier estimates and all post discharge results will be summarized with Kaplan-Meier estimates of event rates. Hazard ratios, confidence interval for the hazard ratios, and p-values may also be presented from a Cox proportional hazards model.

Covariate analyses and variables of interest, as well as possible subgroup analyses of interest, may be performed to gain more clinical insight.

Descriptive statistics will be presented at each assessment, including change from baseline to subsequent time point for selected endpoints. Paired (i.e., patients with available data at both baseline and respective time point) and unpaired data will be presented separately.

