### 7.2 Demographics and Baseline Characteristics

The demographics and baseline characteristics table will contain descriptive summaries of age, sex, race, height, weight, resting blood pressure, STS mortality score, NYHA class, and KCCQ.

THIS DOCUMENT CONTAINS CONFIDENTIAL AND PROPRIETARY INFORMATION OF EDWARDS LIFESCIENCES, LLC. IT MUST NOT BE REPRODUCED OR DISCLOSED TO THIRD PARTIES WITHOUT PRIOR WRITTEN PERMISSION OF EDWARDS LIFESCIENCES, LLC. (This template is required by )

Revision Date: February 28, 2019		Rev		For Use Only by Affiliates of Edwards Lifesciences	Page 11 of 18	
Edwards	Title	Statistical Analysis Plan	for	ACTIVE	2017-05	

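### The gated NYHA I/II test is valid but ignores baseline NYHA class, and may give up power if baseline classes are mixed and prognostic

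*SAP*

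**What the plan says.** SAP 8.4.b specifies a "Superiority test of Device group versus Control group via the Chi-square statistic", run at the two-sided 5% level. What it compares is the "difference in the proportion of subjects with NYHA class I/II at one year". Fisher's exact test is the fallback. Protocol 13.4.4 has the same test. Neither text names a covariate or a stratum.

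On entry, Protocol 6.2 asks for "Symptomatic heart failure patients with measured baseline 6 minute walk test (6MWT) between 150 and 400 meters". No inclusion or exclusion criterion names an NYHA class. Protocol Appendix B defines class II as slight limitation with symptoms on ordinary activity, so a class II patient counts as symptomatic.

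Baseline NYHA is recorded at screening (Protocol 6.6) and tabulated: SAP 7.2 lists "STS mortality score, NYHA class, and KCCQ". Randomization is stratified by site and by ischemic versus non-ischemic disease (SAP 2.3), not by NYHA.

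NYHA is second of eight in the family whose heading in SAP 3.6 begins "Secondary Endpoints – Powered (1 Year". Under SAP 8.4, once an endpoint misses, "no further testing of subsequent endpoints will be conducted".

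Protocol 13.4.1 leaves covariate analyses to be pre-specified in the SAP. SAP 6.1 says only that they "may be performed to gain more clinical insight" and names none.

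**The concern.** The endpoint is an end state, not a change. A patient who enters in class II and stays there counts as a success in either arm. If a sizeable share enter that way, and baseline class predicts class at one year, the outcome varies between patients for reasons unrelated to treatment. An unadjusted test counts that variation as noise; a test stratified by baseline class removes it.

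The plan uses baseline in the neighbouring endpoints. KCCQ, 6MWT and SF-36 (SAP 8.4.c–e) are analysed as differences from baseline, and the responder and patient-success endpoints (SAP 3.7) score NYHA as improvement of at least one class. Among the gated symptom, function and quality-of-life tests, only NYHA leaves baseline out.

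Its position raises the stakes. A miss at NYHA closes six later tests: KCCQ, 6MWT, SF-36, heart failure hospitalization, cardiovascular death and all-cause mortality.

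**Working it through.** **Inputs from the documents.** Allocation 2:1; two-sided alpha 0.05. SAP 8.11 gives two availability figures: 60% of 375 = 225 (75 Control, 150 Device) for co-primary 1, and 300 evaluable (100 Control, 200 Device) for co-primary 2. Both are used.

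**The plan's own two-proportion figure.** Co-primary 1 states >99% power for 10% vs 70%. With 75 and 150, the pooled proportion is (7.5 + 105)/225 = 0.50. Then SE0 = √(0.25 × (1/75 + 1/150)) = 0.0707, SE1 = √(0.09/75 + 0.21/150) = 0.0510, and (0.60 − 1.96 × 0.0707)/0.0510 ≈ 9.0. The figure reproduces. No NYHA power is stated, so there is none to reproduce.

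**Assumed.** The share w in class I/II at baseline, and the one-year I/II rates within each baseline class.

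**Formula.** Power = Φ[(δ − 1.96·SE0)/SE1].
- Chi-square: the SEs use the overall proportions, p(1 − p).
- Stratified: p(1 − p) is replaced by its average over baseline strata, weighted by stratum size. With the same allocation in each stratum, the Cochran-Mantel-Haenszel (CMH) weights are proportional to stratum size, so δ does not change.

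**One case in full** (100:200, w = 40%; Control 80%/35%, Device 90%/50% for baseline I/II and III/IV).
- Overall rates: Control 0.4 × 0.80 + 0.6 × 0.35 = 0.53; Device 0.4 × 0.90 + 0.6 × 0.50 = 0.66; δ = 0.13.
- Chi-square: pooled 0.617; SE0 = √(0.617 × 0.383 × 0.015) = 0.0595; SE1 = √(0.2491/100 + 0.2244/200) = 0.0601; (0.13 − 0.1167)/0.0601 = 0.22; power 59%.
- Stratified: pooled rates 0.867 and 0.45; average variance 0.4 × 0.1156 + 0.6 × 0.2475 = 0.1947; SE0 = √(0.1947 × 0.015) = 0.0540; SE1 = √(0.2005/100 + 0.186/200) = 0.0542; (0.13 − 0.1059)/0.0542 = 0.44; power 67%.
- Simulation (20,000 trials) gives 59% and 67%.

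**Across assumptions** (first three rows simulated, 20,000 trials per cell; last row by the formula):

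| One-year I/II rates by baseline class (I/II, III/IV) | Control gap | w | 75:150, chi-square → CMH | 100:200, chi-square → CMH |
|---|---|---|---|---|
| 75/30 vs 85/45 | 45 points | 35% | 48% → 54% | 59% → 66% |
| 85/25 vs 92/40 | 60 points | 35% | 42% → 53% | 53% → 65% |
| 80/35 vs 90/50 | 45 points | 40% | 47% → 55% | 59% → 67% |
| 70/45 vs 80/60 | 25 points | 35% | 49% → 51% | 61% → 63% |

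For w from 20% to 50%, the gain is about 3–16 points with the 45–60-point gaps and about 1–2 points with the 25-point gap. With w = 0 the gain is nil, and in simulation stratifying costs less than 1 point.

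**Dilution is separate from noise.** Suppose the device does nothing in class II (85% vs 85%) and gives 35% vs 55% in III/IV. The overall difference falls from 0.20 to 0.6 × 0.20 = 0.12 at 40% class II. At 100:200 the chi-square power is 92%, 76%, 53% and 31% at 0, 20, 40 and 60% class II. CMH reaches only 80%, 60% and 34% at the last three.

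**Type I error.** Under the null with 20–60% class II, simulated one-sided error is 0.026–0.027 (chi-square) and 0.024–0.026 (CMH). With four strata (NYHA by etiology) it also stays near 0.025.

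**The case against.** The strongest reply is that nothing here is wrong. The pre-specified chi-square tests exactly the hypothesis stated, and in a randomized trial it is valid. That stands.

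The power loss is not documented either. Entry requires symptomatic heart failure, MR of at least 3+, a raised natriuretic peptide or recent heart failure hospitalization, and a limited walk. These criteria may keep the class II share low. The larger gains also need strongly prognostic strata; at a 25-point gap they shrink to 1–2 points. Both points stand, and they are why the size is given as a range.

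The fix does not rescue the gate. In the 35% scenarios with the larger gaps, power after stratifying is still only about 53–66%. That stands too.

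NYHA change is examined elsewhere, in the responder and patient-success endpoints, and covariate analyses are permitted. Those analyses are descriptive or optional and cannot stand in for the gated test, so this part does not answer the point.

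**Conclusion.** The point holds as a conditional efficiency weakness. The test ignores a baseline measure already held on the same scale as the outcome, and nothing at entry prevents mixed baseline classes. Stratifying gains from nothing to about 16 points of power, depending on a baseline mix and one-year rates that the documents do not give, and costs almost nothing when no class I/II patients enrol.

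Three stronger readings are not supported:
- A reader might infer that the test is biased or its alpha inflated. It is not.
- A reader might take the power loss as fact, or baseline NYHA as the strongest predictor of NYHA at one year. Both are plausible, but the documents show neither.
- A reader might infer that stratifying restores the power lost by enrolling class II patients. It removes noise only; the dilution remains.

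No stated figure is contradicted. The family is labelled as powered, yet no NYHA rate, effect or power appears.

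**What to change.** In SAP 8.4.b and Protocol 13.4.4, replace the chi-square with a CMH test stratified by baseline NYHA (I/II vs III/IV) and by ischemic versus non-ischemic disease, which is already a randomization stratum. Report the stratified risk difference with its 95% CI. The Fisher fallback needs a stratified counterpart for sparse strata. State the assumed baseline mix, the NYHA rates and the resulting power.

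Make the change before unblinding; an adjustment chosen afterwards could not serve as the confirmatory gate. The cost is wording in two documents: no new data, visits or patients.
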